5.4.3.2 Ovarian Cancer Cohort

The interim analysis will be based on at least 6 and most 16 patients having completed from 9 up to 27 weeks of treatment (3 to 9 cycles) in the ovarian cancer cohort.

The second stage will continue if at least 2 patients (out of 6-16 patients) respond in the overall tumor response assessed through RECIST v1.1. (provided the DMC decides not to stop the second stage because of safety issues).

5.4.3.3 Cervical Cancer Cohort

The interim analysis will be based on at least 6 and most 15 patients having completed from 9 up to 27 weeks of treatment (3 to 9 cycles) in the cervical cancer cohort.

The second stage will continue if at least 2 patients (out of 6-16 patients) respond in the overall tumor response assessed through RECIST v1.1. (provided the DMC decides not to stop the second stage because of safety issues).

5.4.4 *Multiple Comparisons/Multiplicity*

The four cohorts will be handled separately, no adjustment for multiple comparisons will be made between cohorts. No adjustment for multiple comparisons will be performed within a cohort as there is only one primary endpoint in each of the three main cohorts.

For the secondary efficacy variables, no statistical inference will be performed. Thus, no adjustment for multiple comparisons will be made.

5.4.5 *Examination of Subgroups*

No pre-defined analysis on subgroups are planned.

5.5 *Patient Disposition Summary*

Descriptive summaries for continuous data and for categorical data will be provided in accordance with Section 5.3 if other not stated.

5.5.1 *Patient Disposition*

Number of patients screened, enrolled, discontinued for treatment (by reason), continuing in follow-up, and discontinued from the study (by reason) will be summarized by cancer cohort.

5.5.2 *Protocol Deviations*

Protocol deviations will be displayed in listings.

5.5.3 *Demographic and Baseline Characteristics*

Demographics and baseline characteristics (gender, age, ethnicity, race, height, weight and body surface area) will be presented as a table for the screening visit.

5.5.4 *Medical History*

Medical history and medical conditions ongoing at Screening will be coded by system organ class (SOC) and preferred term (PT) using MedDRA (version 20.0) and presented as number and percentage of patients in each SOC and PT by cancer cohort and in total over cohorts.

5.5.5 *Prior and Concomitant Medications*

Prior and concomitant medication will be coded according to the WHO-Drug Dictionary Enhanced (Version Mar 2017) and ATC classification. Prior and concomitant medication will be reported as a listing for all enrolled patients and tabulated by ACT level 1 and level 3 by cancer cohort and in total over cohorts.

Prior anti cancer therapies, prior medications and concomitant medications will be tabulated separately.

5.5.6 *Exposure to Study Treatment*

The Investigational products will be administered as IV infusions by study staff and administration information will be recorded in the appropriate CRF.

The following variables will be derived for birinapant and Pembrolizumab separately:

- Cumulative dose = Sum of all administered doses.
- Treatment duration (weeks) = (Date of last dose – date of first dose + planned treatment duration(days))/7.
- Dose intensity = Cumulative dose/Treatment duration
- Relative dose intensity (%) = 100*Dose intensity/Planned dose intensity

Planned treatment duration(days) is 21 days for Pembrolizab and 13 days (21-8) for birinapant (this is the number of days between the last dose of a treatment cycle and the first dose in the subsequent cycle).

The unit of the dose will be in milligram (mg) for Pembrolizumab and in mg/m² for birinapant. For birinapant, the total dose in ‘mg’ is divided by the patient body surface area (m²) to get dose expressed as mg/ m².

Cumulative dose, treatment duration, dose intensity, relative dose intensity, number of infusions administered, number of cycles started, and infusion time per administration will be summarized using descriptive statistics by cohort, treatment (Pembrolizumab) and cycle (cycle 1 and the minimum and maximum observed value during the subsequent cycles) and in total over cycles as appropriate.

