The primary objective will be evaluated using Simon's two-stage design. The null hypothesis that the true ORR is (5%, 7% and 10% for colorectal cancer, ovarian cancer and cervical cancer, respectively) will be tested against a one-sided alternative. The design yields a type I error rate of 5% and power of 80% for each of the three indications individually. No correction for multiplicity will be done. In addition to tabulate the result of the statistical tests, results will be summarized descriptively.

Various solid tumors cohort: Safety

The safety and tolerability of pembrolizumab and birinapant will be based on results of reported SAEs, AEs, vital sign measurements, physical examinations, clinical laboratory information, ECOG performance status, and concomitant medications. Safety data will be summarized descriptively. Exposure to study drug and reasons for discontinuation will be tabulated.

Adverse events will be coded using the current *Medical Dictionary for Regulated Activities* (MedDRA) classification system, and will be summarized by system organ class and preferred term.

Additional safety analyses may be determined in order to most clearly describe toxicity rates and to further define the

safety profile of pembrolizumab and birinapant.

Secondary Endpoints:

Cohorts in colorectal cancer, ovarian cancer and cervical cancer: Safety

The safety and tolerability of pembrolizumab and birinapant will be based on results of reported SAEs, AEs, vital sign measurements, physical examinations, clinical laboratory information, ECOG performance status, and concomitant medications. Safety data will be summarized descriptively by cohort and also summarized descriptively over cohorts within each of the two phases of the protocol. Exposure to study drug and reasons for discontinuation will be tabulated.

Adverse events will be coded using the current *Medical Dictionary for Regulated Activities* (MedDRA) classification system, and will be summarized by system organ class and preferred term.

Additional safety analyses may be determined in order to most clearly describe toxicity rates and to further define the safety profile of pembrolizumab and birinapant.

All Cohorts: Clinical Activity

Efficacy, as defined by PFS, CBR, Time to response and Duration of response, will be assessed through RECIST v 1.1 and until response or progression. Overall survival will also be assessed.

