3.3.1.2 Dose expansion phase

The dose expansion phase will comprise 4 cohorts of 26-30 patients, as follows:

1. Colorectal cancer (28 patients will be recruited)
2. Ovarian cancer (27 patients will be recruited)
3. Cervical cancer (26 patients will be recruited)
4. Various solid tumors (30 patients will be recruited, including 5 patients with each of the 6 following tumor types: (Small cell lung cancer; Cholangiocarcinoma; Gastroesophageal carcinoma; Mesothelioma; Head and Neck Squamous Cell Carcinoma (HNSCC)-checkpoint inhibitor-naïve; and HNSCC checkpoint inhibitor-experienced)

A Simon's 2-stage design (Simon 1989) will be used for each of the cohorts in colorectal cancer, ovarian cancer and cervical cancer, as outlined in Table 4. A predefined interim analysis allowing stopping each of these cohorts for futility and safety will be conducted in the first stage to limit undue exposure before further inclusion into a given cohort.

The interim analyses will be based on at least 6 and most 13 patients having completed from 9 up to 27 weeks of treatment (3 to 9 cycles) in the colorectal cancer cohort and based on at least 6 and at most 16 and 15 patients in the ovarian cancer cohort and cervical cancer cohort, respectively.

The Simon's two-stage design as outlined in Table 4 yields a type I error rate of 0.05 and statistical power of 0.80 for each of the three main cohorts described above using a one-sided test when the true response rate is 20% for colorectal cancer, 25% for ovarian cancer and 30% for cervical cancer. No formal sample size or power calculation will be performed for the fourth cohort.

Note that one additional patient will be included in each cohort compared to what is stated in Table 4. This patient will only be included in the interim analysis in case a patient drops out in that cohort. Thus, the number of included patients in each cohort will be 27+ 1 (CRC), 26+1 (ovarian) and 25+1 (cervical). In all cases this extra patient will be included in the main/end analysis. If the predefined level for success in a given cohort is reached prior to the stipulated number of patients being enrolled/completed, enrollment in that cohort may be discontinued.

4. Assessments

An overview of the time points of measurements for each assessment is given in Table 5 (Schedule of Study Procedures and Assessments) in Appendix 1.

4.1 *Disposition and Other Supporting Assessments*

4.1.1 *Patient Compliance*

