5.6.1 Primary Efficacy Analysis

The primary endpoint will be summarized for the Efficacy Evaluable Population in accordance with Section 5.3.

The primary efficacy analysis for each of the three main cohorts in the dose expansion phase of the protocol will be evaluated using Simon’s two-stage design (Simon 1989). The null hypothesis that the true response rate (π) is π_0 will be tested against the one-sided alternative $H_A: \pi > \pi_0$ in each of the three cohorts with π_0 , π_1 , n_1 , n , r_1 and r_2 as in Table 4 as follows. In the first stage, n_1 patients will be accrued. If there are r_1 or fewer responses in these n_1 patients, the cohort will be stopped and the p-value for the test will be reported as not significant (no p-value will be calculated). Otherwise, $n - n_1$ additional patients will be accrued for a total of n patients. The null hypothesis will be rejected if r_2+1 or more responses are observed in n patients.

Table 4 Simon’s two-stage design settings in each of the three main cohorts

Indication	Response rate (ORR)		n_1 (# patient in the 1 st stage)	n (Total #patients)	r_1 (Continue with stage 2 if $>r_1$ responses in stage 1)	r_2 (p-value ≤ 0.05 if $>r_2$ responses after stage 2)
	Poor drug (π_0)	Good drug (π_1)				
Colorectal cancer	$\leq 5\%$	$\geq 20\%$	13	27	0	3

Ovarian cancer	$\leq 7\%$	$\geq 25\%$	16	26	1	4
Cervical cancer	$\leq 10\%$	$\geq 30\%$	15	25	1	5

In case the total number of evaluable patients do not equal the planned number of patients (n in Table 4), the statistical inference of the ORR will take account of the actual total number of evaluable patients, n^* , as suggested in Koyama and Chen (2007). With a modified stage 2 sample size, the p-value will be calculated as follows.

- i. Find π^* such that $P_{\pi}(X_2 > r_2 - x_1 | n_2) = P_{\pi_0}(X_2 \geq x_2 | n_2^*)$
- ii. Compute the p-value by

$$\sum_{x=r_1+1}^{n_1} P_{\pi_0}(X_1 = x | n_1) A(x, n_2, \pi^*)$$

Here $n_2 (= n - n_1)$ denotes the planned number of patients in the second stage, n_2^* the actual number of patients in the second stage and X_2 denotes the number of responses among those n_2 patients. The p-value will be calculated as above even if $n_2^* = n_2$. In that case it simplifies to the original Simon's 2-stage design with rejection regions as in Table 4.

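### SAP 5.4.3.3 states the cervical continue rule on 6-16 patients, although the cervical first stage is capped at 15 everywhere else; the range should read 6-15

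*SAP*

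**What the plan says.** SAP 5.4.3.3 gives two upper limits for the same interim analysis. Its first sentence reads "The interim analysis will be based on at least 6 and most 15 patients having completed from 9 up to 27 weeks of treatment". The sentence that carries the decision reads "The second stage will continue if at least 2 patients (out of 6-16 patients) respond".

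The other places agree on 15 for cervical cancer:

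- SAP 3.3.1.2 has the interim "based on at least 6 and at most 16 and 15 patients in the ovarian cancer cohort and cervical cancer cohort, respectively".
- SAP Table 4 (section 5.6.1) sets the cervical design at n1 = 15, n = 25, r1 = 1, r2 = 5, for response rates of 10% and 30%.
- Protocol 12.2 and Protocol Table 17 give the same first-stage number.

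The cohort with 16 is ovarian. SAP 5.4.3.2 reads "The interim analysis will be based on at least 6 and most 16 patients having completed from 9 up to 27 weeks of treatment" and then applies its own rule of at least 2 responders to 6-16 patients.

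SAP 3.3.1.2 and Protocol 12.2 and 12.7 also provide for one extra patient per cohort (25+1 for cervical). That patient counts at the interim only if someone drops out, and always counts in the final analysis.

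**The concern.** The decision sentence tells the Data Monitoring Committee when to open the second stage, so its denominator should have one reading before any response is seen. As printed, it has two. If exactly 1 of 15 patients has responded and a 16th patient who is also counted responds, the first sentence and Table 4 say stop, while the decision sentence says continue. In an open-label, single-arm trial, choosing between 15 and 16 at that moment would look driven by the data.

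There is also a mismatch with the final inference. The p-value formula in SAP 5.6.1 sums over first-stage results up to n1 and adjusts only for a changed second-stage size. It offers no method for a first stage of 16 when n1 is 15.

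**Working it through.** **Which figure is out of line.** Comparing the stated maximum with the range in the decision sentence, cohort by cohort:

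| Cohort | Interim maximum | Table 4 n1 | Range in decision sentence |
|---|---|---|---|
| Colorectal (SAP 5.4.3.1) | 13 | 13 | 6-13 |
| Ovarian (SAP 5.4.3.2) | 16 | 16 | 6-16 |
| Cervical (SAP 5.4.3.3) | 15 | 15 | 6-16 |

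Only the cervical range departs from its own maximum, and it equals the ovarian range. If 16 meant 15 plus the extra patient, the other two would read 6-14 and 6-17. They do not.

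**Inputs** (SAP Table 4, cervical): p0 = 0.10, p1 = 0.30, n1 = 15, r1 = 1, n = 25, r2 = 5.

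**Formulas** (exact binomial):

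- Early stopping: P(X1 ≤ 1) = (1−p)^n1 + n1·p·(1−p)^(n1−1).
- Rejecting the null: sum over x from r1+1 to n1 of P(X1 = x) · P(X2 ≥ r2+1−x), with X2 binomial on n − n1 patients.

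**Reproducing the plan's figure.** With n1 = 15 and n = 25, the type I error is 0.0328 and the power 0.8017. This agrees with the stated 0.05 (read as a cap, because the test is discrete) and 0.80. The threshold of at least 2 responders agrees with r1 = 1.

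**Early stopping with 15 and with 16:**

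- p = 0.10, n1 = 15: 0.9^15 + 15·0.1·0.9^14 = 0.2059 + 0.3432 = 0.549
- p = 0.10, n1 = 16: 0.9^16 + 16·0.1·0.9^15 = 0.1853 + 0.3294 = 0.515
- p = 0.30, n1 = 15: 0.7^15 + 15·0.3·0.7^14 = 0.0047 + 0.0305 = 0.035
- p = 0.30, n1 = 16: 0.7^16 + 16·0.3·0.7^15 = 0.0033 + 0.0228 = 0.026

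**Probability that the two readings give opposite decisions**, P(exactly 1 of 15) · p:

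- p = 0.10: 0.3432 · 0.10 = 0.034
- p = 0.30: 0.0305 · 0.30 = 0.009

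These equal the differences between the stopping probabilities above.

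**Type I error and power:**

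| Total n | n1 | Type I error | Power |
|---|---|---|---|
| 25 | 15 | 0.0328 | 0.8017 |
| 25 | 16 | 0.0331 | 0.8042 |
| 26 | 15 | 0.0389 | 0.8306 |
| 26 | 16 | 0.0393 | 0.8338 |

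The rows with 26 add the extra patient to the final analysis and keep r2 = 5 unadjusted. The choice between 15 and 16 matters no more there than at 25.

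**The case against.** The best defence is that no careful reader is left without a governing number. The sentence just before the rule caps the interim at 15. SAP 5.6.1 states the formal rule on the n1 patients of Table 4. Both documents confine the extra patient to replacing a dropout. On this view the slip sits in one parenthesis and has no practical effect. Most of that stands: the intended figure is clear, and the error rates barely move. It does not remove the contradiction, because the wrong figure is in the sentence that states the decision.

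Two stronger readings are tempting, and the documents do not support them. A reader might infer that the cervical design rests on a wrong first-stage number. It does not: n1 = 15 is stated consistently in the design tables and reproduces the stated power. A reader might also infer that a 16th patient will have data at the interim and will be counted without any dropout. The documents place one extra patient in the cohort total; they do not say that this patient is the 16th enrolled or is on study at the interim. The dropout condition bars counting that patient otherwise.

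**Conclusion.** The range in the cervical decision sentence is wrong as written and should match n1 = 15. That it was carried over from the ovarian paragraph is the likely explanation, but an inference.

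The consequence is limited. The two readings can lead to opposite decisions with probability of about 3.4% at a true response rate of 10% and 0.9% at 30%, and only if a 16th patient has an evaluable response at the interim. Type I error stays below 0.05 and power stays at about 0.80 under either reading. These figures assume independent responses, an interim held at the full first-stage number, and r1 and r2 as in Table 4.

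This is a consistency correction to a prespecified stopping rule. It does not touch the lower bound of 6, which all three cohorts share and which has a larger numerical effect: if the rule of 2 responders were applied as a final stop at 6 patients, the chance of stopping at a true rate of 30% would be 42.0%, and power would be 0.53 with a total of 25.

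**What to change.** In the decision sentence of SAP 5.4.3.3, change 6-16 to 6-15. Keep the range: putting 15 alone would delete the lower bound and create a new conflict with the sentence before it. The condition on the extra patient is already stated in SAP 3.3.1.2 and needs no new wording. The cost is one figure in the SAP. The protocol already gives 15 and needs no amendment.

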3.2.2 Design Rationale Dose Expansion Phase Study Design

The phase 2a part of this study is constituted by a number of individual single-arm treatment cohorts in order to obtain an estimate of the degree of the anti-tumor effect. Simon's two-stage design is used for the dose expansion component of this study. The intent is to expose as few patients as possible to an ineffective drug. It is ethically imperative that the study is terminated if the drug is shown to have little or no anti-tumor activity. Simon's two-stage design gives the option to stop development of the drug in a given indication after the first or second stage if insufficient activity is demonstrated. The design also enables an early readout of sufficiently promising activity to warrant further investigation in a phase 3 study. The design of the various solid tumors cohort will limit undue exposure in any of the selected tumor types by virtue of the fact that it limits the number of enrolled patients to five in each tumor type. Following any positive results, it is the sponsor may consider the initiation of an expansion cohort in any of the tumor types included in the various solid tumor cohort, following submission of a protocol amendment. For further information of the patient population and the specific rationale for including these groups with high unmet medical need in this trial, refer to [section 1.5](#).

The dose of birinapant is the RP2D chosen from the dose escalation part of the study. All patients in this part of study will therefore receive birinapant at a dose within the expected therapeutic range with the possibility to halt dosing as described in [section 5.5](#) in the case of adverse event and may reinitiate at a lower dose according to the schema in [section 5.5.1](#). The dose of pembrolizumab is the manufacturer's standard recommended dose used in approved indications. Available preclinical data for birinapant discussed in section 1.1 indicates the potential for an added clinical benefit with the combination of birinapant and pembrolizumab. Birinapant has a favorable safety profile based on data from previous trials, which indicates that the combination has a low risk of generating unacceptable toxicity.

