3.4.2.2 Secondary Endpoints

Safety and tolerability will be assessed in colorectal cancer, ovarian cancer and cervical cancer by monitoring:

- Incidence and severity of adverse events (AEs) experienced by patients receiving birinapant in combination with pembrolizumab.
- Incidence and magnitude of clinically significant changes in clinical laboratory parameters experienced by patients receiving birinapant and pembrolizumab, or overall pattern of shifts by treatment group in individual laboratory values suggestive of possible trends, but not necessarily establishing, clinical abnormality.
- Incidence and severity of clinically significant adverse findings in vital signs, electrocardiogram (ECGs), and other physical examination parameters among patients receiving birinapant and pembrolizumab.

Clinical Activity: Tumor response will be assessed in all four cohorts by monitoring:

- Progression Free Survival (PFS)
- Clinical Benefit Rate (CBR) defined as CR+PR+SD
- Time to response
- Duration of response
- Overall Survival (OS)

Measures of tumor response will be evaluated using RECIST v1.1 until response or progression and will be subsequently analyzed through iRECIST as an exploratory endpoint (see below).

3.4.2.3 *Exploratory endpoints*

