4.2.2.3 Exploratory Efficacy Variable

Tumor response and progression evaluated in all four cohorts using iRECIST:

- Overall response
- iBOR
- Duration of iBOR
- Time to iCPD
- Clinical Benefit Rate (CBR) defined as iCR+iPR+iSD
- Time to response
- Duration of response

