5.3 General Principles for Presenting Study Data

All statistical analyses will be performed at SDS using SAS® (Version 9.3 or higher, SAS Institute Inc., Cary, NC, USA). All statistical analyses will be performed after this SAP is finalised and approved and the study database is locked.

Continuous data will be summarized using descriptive statistics where the following parameters will be reported:

- Number of observations (n),
- Mean,
- Median,
- Standard deviation (SD),

- Range (Min, Max)

Categorical data will be presented as the number and percentage of patients.

Time to event endpoints defined in Section 4.2.3 (e.g. duration of response, OS and time to iCPD) will be analysed using Kaplan-Meier methods taking censoring into account. The Kaplan-Meier plot and corresponding estimate of the median value with 95% confidence interval will be reported.

All tests will be one-sided and performed at the 5% significance level. When reporting the results of significance tests, p-values will be reported together with 2-sided 90% confidence intervals.

Throughout the report, the number of decimal places given for the summary statistics; mean, STD, confidence interval and median values will exceed that of the source data by one. Minimum and maximum will have the same number of decimal places as the source data. For relative frequencies, integer with one decimal and %-sign will be presented and for p-values four (three) decimals will be reported.

Percentages will be based on number of patients with data at a certain time point with the exception of presentations of medical history, medications and AEs where the percentages will be based on the number of patients in the study population.

In general, all data will be listed, sorted by phase of study, cohort and patient, and when appropriate by cycle within patient. All summary tables will be structured with a column for cohort and will be annotated with the total population size relevant to that table/cohort, including any missing observations. Summary tables will include summaries for visits for Cycle 1 (Screening, Day 1 pre dose, Day 1 post dose, Day 8 pre dose, Day 8 post dose and Day 22 End of Cycle 1 as appropriate) whereas subsequent cycles will be summarized with summary statistics for the minimum and maximum observed value during the subsequent cycles.

The two phases of the study will be summarized separately. In addition, cohorts from phase 1 and phase 2 may be combined and summarized if appropriate.

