5.6.2 Secondary Efficacy Analyses

The secondary endpoints will be summarized with descriptive statistics in accordance with Section 5.3 for the Efficacy Evaluable Population.

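### Planned efficacy tables pool the six tumor types of the various-solid-tumors cohort, although results in a single type may prompt an expansion cohort

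*SAP*

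**What the plan says.** The fourth expansion cohort has 30 patients: 5 each with small cell lung cancer, cholangiocarcinoma, gastroesophageal carcinoma, mesothelioma, checkpoint-naive HNSCC and checkpoint-experienced HNSCC (Protocol 3.1.2, SAP 3.1.2). Its primary objective is safety. Efficacy is secondary and exploratory: Protocol 3.4.2.2 states "Clinical Activity: Tumor response will be assessed in all four cohorts by monitoring", followed by PFS, CBR, time to response, duration of response and OS, and SAP 4.2.2.3 adds "Tumor response and progression evaluated in all four cohorts using iRECIST".

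Protocol 3.2.2 says that after positive results the sponsor "may consider the initiation of an expansion cohort in any of the tumor types included in the various solid tumor cohort", by protocol amendment.

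On presentation, SAP 5.3 says "All summary tables will be structured with a column for cohort". SAP 5.4.4 says "The four cohorts will be handled separately, no adjustment for multiple comparisons will be made between cohorts". SAP 5.6.2 says "The secondary endpoints will be summarized with descriptive statistics in accordance with Section 5.3 for the Efficacy Evaluable Population", and 5.6.3 treats the exploratory endpoints the same way. SAP 5.4.5 and 5.6.4 both say "No pre-defined analysis on subgroups are planned". For listings, 5.3 says "In general, all data will be listed, sorted by phase of study, cohort and patient".

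**The concern.** Tumor type is the working unit of this cohort. Enrollment is capped at five per type, each type has its own eligibility criterion, and the only follow-on action the protocol names is an expansion in a single type. The SAP's unit of tabulation is the cohort. Followed as written, the report would show one CBR, one PFS curve and one OS curve over six diseases. One of the six groups must already have progressed on an anti-PD-1 or anti-PD-L1 antibody, while the others must not have received one.

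The result that would inform the action in Protocol 3.2.2 would then be missing from the planned tables. If someone assembled it afterwards, the best of six small groups could be picked out with no pre-specified display and no warning about how often chance alone produces such a group.

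**Working it through.** **Composition.** 6 x 5 = 30 for this cohort, and 28 + 27 + 26 + 30 = 111 for the expansion phase. Both agree with the documents. No power is stated for this cohort, so there is no power figure to reproduce.

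**Expected pooled response rate with no birinapant effect.** Inputs are the pembrolizumab-alone ORRs in Protocol 1.5.4:

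| Group | ORR | Note |
|---|---|---|
| SCLC | 33% | PD-L1-expressing patients |
| Cholangiocarcinoma | 17% | biliary tract, PD-L1-positive patients |
| Gastroesophageal | 30% | esophageal study; 11% in the gastric/GEJ cohort behind the accelerated approval |
| Mesothelioma | 20% | PD-L1-expressing patients |
| HNSCC, checkpoint-naive | 16% | previously treated patients |
| HNSCC, checkpoint-experienced | 0-16% | assumption; no figure is given |

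With 5 patients per type, the pooled expectation is the simple mean of the six rates:
- Gastroesophageal at 30%: (33 + 17 + 30 + 20 + 16 + 0)/6 = 116/6 = 19.3%, up to 132/6 = 22.0%.
- Gastroesophageal at 11%: (33 + 17 + 11 + 20 + 16 + 0)/6 = 97/6 = 16.2%, up to 113/6 = 18.8%.

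The range is therefore about 16-22%, or roughly 5 to 7 responses in 30. The protocol also cites 22% for a gastric/GEJ study; using it gives 108/6 = 18.0% to 124/6 = 20.7%, inside this range. The cohort requires a tissue sample for PD-L1 analysis but not a positive result, so the true expectation may be lower.

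**What a pooled 6/30 conveys.** Exact (Clopper-Pearson) limits are the Beta(x, n-x+1) quantile at alpha/2 and the Beta(x+1, n-x) quantile at 1-alpha/2. For 6/30 these give 7.7-38.6% at 95% and 9.1-35.7% at 90%. The row is identical for 1/5 in each of six types (6 x 1 = 6) and for 5/5 in one type plus one response in another (5 + 1 = 6). Only the first pattern looks like pembrolizumab alone.

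**What a by-type table can and cannot show.** Exact 90% intervals with n = 5:

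| Responders | 90% CI |
|---|---|
| 0/5 | 0-45.1% |
| 1/5 | 1.0-65.7% |
| 2/5 | 7.6-81.1% |
| 3/5 | 18.9-92.4% |

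For one named type at a true 20%:
- P(3 or more of 5) = 10(0.2^3)(0.8^2) + 5(0.2^4)(0.8) + 0.2^5 = 0.0512 + 0.0064 + 0.0003 = 0.058.

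For at least one of six types, all at 20%:
- 3/5 or more: 1 - (1 - 0.058)^6 = 0.30.
- 2/5 or more, with 0.263 per type: 1 - (1 - 0.263)^6 = 0.84.

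**The case against.** The strongest reply is that nothing formal depends on this table. The cohort's primary aim is safety, it has no sample-size basis, and no inference is planned on secondary efficacy. Protocol 3.2.2 is permissive, sets no threshold and requires an amendment. That stands, and it limits the weight of the point: a reader might infer that the protocol bases new cohorts on by-type results, but it says only that the sponsor may consider one.

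A reader might also infer that the decision cannot be made at all from the planned output. That goes too far. Protocol 12.1 and SAP 5.3 put the data in patient listings, and responders can be counted by hand among 30 patients. The listings are not sorted by tumor type, however, and a hand count is not a planned summary.

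A third tempting reading is that RECIST 1.1 ORR is not assessed in this cohort. It is absent from the secondary list, but Protocol 12.7 names ORR by RECIST 1.1 and iRECIST without limiting it to particular cohorts. Time to response and duration of response, planned for all four cohorts, also require confirmed responders to be identified. What is lacking is a clear statement in the SAP.

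Finally, the mock-up tables are a separate document (SAP 1) and might split the column. No passage says outright that the six types will be combined; this follows from 5.3 together with 5.4.5 and 5.6.4. The SAP text does not require a split.

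**Conclusion.** The point holds for the planned summary tables. The SAP gives this cohort one efficacy column and declines subgroup analysis, while the protocol contemplates action on a single type. A pooled rate cannot be interpreted for that purpose: about 16-22% is expected from pembrolizumab alone, and the same 6/30 covers very different by-type patterns. The range rests on the protocol's cited rates, on equal groups of 5, and on the assumed 0-16% for checkpoint-experienced HNSCC.

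A by-type table would be descriptive only. A reader might take the 6% chance of 3/5 or more at a true 20% as strong evidence for whichever type reaches it, but that figure belongs to one type named in advance. For at least one of six it is about 30%, which is a reason to fix the display and its caveat beforehand. The primary analyses of the three main cohorts are unaffected.

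**What to change.** In SAP 5.3 and 5.6.2, add one descriptive table for this cohort with a row for each of the six tumor types:
- confirmed RECIST 1.1 responders over n, with an exact CI at a stated level; n is the number in the Efficacy Evaluable Population and may be below 5;
- best overall response;
- CBR.

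Sort the PFS and OS listings for this cohort by tumor type. State that no testing is done, that five patients give very wide intervals (3/5: 90% CI 19-92%), and that at a true 20% in all types the chance of at least one reaching 3/5 or more is about 30%. Exempt this table from the no-subgroup statements in 5.4.5 and 5.6.4. State that RECIST 1.1 ORR is summarized descriptively for this cohort, in line with Protocol 12.7. Keep pooling for safety.

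The cost is some SAP wording, one table and a changed sort order, all from data already collected.
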